11.1 Study Hypothesis

- Null: the sum of the probability that a subject assigned to the 5-day arm will have a higher DOOR than if assigned to the 10-day arm plus one-half the probability of equal DOORs is 50% (i.e., no difference in DOOR).

11.2 Sample Size Considerations

The primary study sample size is based on a superiority test of the null hypothesis in 11.1, under an assumed alternative hypothesis that the sum of the probability that a subject assigned to the 5-day arm will have a higher DOOR than if assigned to the 10-day arm plus one-half the probability of equal DOORs is 60% ($p=60\%$).

A sample size of 360 (180 per arm) provides 90% power using a 2-sided $\alpha=0.05$ with a Wilcoxon Mann-Whitney U test. If $p=65\%$ or 70% , then a total sample size of 160 (80 per arm) or 90 (45 per arm), respectively, would be required. The sample size is inflated by ~10% based on an estimate from a similar study, in order to account for loss to follow-up resulting in a total sample size of 400 (200/arm).

11.3 Planned Interim Analyses

11.3.1 Safety Review

A Data Safety Monitoring Board (DSMB) appointed by NIAID will monitor this protocol. Interim safety review may include enrollment and demographic information, medical history, concomitant medications, physical assessments, dosing, and protocol specific SAEs and SUSAR. Additional data may be requested by the DSMB, and interim statistical reports may be generated as deemed necessary and appropriate by DMID. The DSMB may receive data in aggregate and presented by treatment group. The DSMB will meet and review this data at scheduled time points or ad hoc as needed during the study as defined in the DSMB charter. As an outcome of each

review/meeting, the DSMB will make a recommendation as to the advisability of proceeding with the study or to modify or terminate the study.

Additionally, the study will be monitored to determine if any of the halting rules described in Section 9.5 are met.

11.3.1 Interim Analysis of Efficacy, Futility, and Safety

One interim analysis, described below, will be performed and reported to the DSMB after at least 30% of the targeted subjects have completed the study. The interim analysis will inform DSMB decisions regarding stopping early for efficacy, futility, or safety.

For the interim analysis, a snapshot of the study database will be unblinded and used to conduct analyses as follows. An ITT analysis including all enrolled subjects in the snapshot of the study database will be performed, testing the null hypothesis provided in Section 11.1 using the methods described in Section 11.4.1, with the modification that the Haybittle-Peto boundary ($p < 0.001$) will be used when concluding statistical significance. The study may be stopped early for efficacy only if statistical significance is detected in that test. In the event of statistical significance, sensitivity analyses using complete case and according-to-protocol cohorts (CC-V1 and ATP-V1, as described below) as well as worst case analyses will be included in the DSMB report to further guide decisions for stopping for efficacy.

A 95% confidence interval for the probability that a randomly selected subject will have a better DOOR if assigned to the 5-day strategy (vs. the standard strategy) will be estimated but not used to inform DSMB decisions about stopping early for efficacy. Predicted interval plots (PIPS)^{12,13} will be constructed to provide the DSMB with a prediction of the trial results were the trial to continue as planned under varying assumptions regarding future data (e.g., current trend continues, null hypothesis is true, alternative hypothesis is true).

The DSMB will also be provided with the following:

1. For subjects that have completed Outcome Assessment Visit #1 and have received at least one dose of study product, a between arm difference in the overall outcome (DOOR) via a cumulative difference plot with respective confidence bands for Outcome Assessment Visit #1
2. For subjects that have completed Outcome Assessment Visit #1 and have received at least one dose of study product, a forest plot of 95% confidence intervals for the risk difference of adequate clinical response as well as the following interventions for persistent or worsening pneumonia: (1) ED/clinic visits, (2) hospitalizations, (3) surgical procedures, and (4) non-study systemic antibiotics at Outcome Assessment Visit #1.
3. For subjects that have completed Outcome Assessment Visit #1 and have received at least one dose of study product, a forest plot of 95% confidence intervals for the risk difference of lack of resolution of symptoms as well as the following: (1) Oral, rectal, axillary or tympanic temperature $\geq 38.3^{\circ}\text{C}$ (100.9°F), confirmed by repeat measurement after at least 15 minutes, in the 24 hours preceding Outcome Assessment Visit #1, unless attributed to a new process that is unrelated to the prior diagnosis of pneumonia; (2) Elevated respiratory rate (RR >50

breaths/minute for children <24 months of age and >40 breaths/minute for children 24-71 months of age) at Outcome Assessment Visit #1, and (3) Presence of cough Grade 2 or 3 at Outcome Assessment Visit #1.

4. For subjects that have completed Outcome Assessment Visit #1 and have received at least one dose of study product, a forest plot of 95% confidence intervals for the risk difference of each solicited event and with the risk difference of any solicited event, for each severity threshold (mild or greater, moderate or greater, or severe) for Outcome Assessment Visit #1.

11.4 Final Analysis Plan

The primary analysis of the primary endpoint will be performed according to an intention-to-treat (ITT) approach and include all randomized subjects. As (secondary) sensitivity analyses of the primary endpoint, complete case analyses using the CC-V1 / ATP-V1 cohorts (defined below) and a worst case analysis using the ITT cohort of the primary endpoint will be performed. Additional analyses may be performed and are described in detail in the Statistical Analysis Plan.

Intention-to-Treat Cohort: All randomized participants, analyzed as randomized. Subjects that have not received at least one dose of study product will have adequate clinical response and its sub-components treated as missing.

Complete Case Cohorts (CC): Subjects in a CC analysis are analyzed as randomized, but excluded from analysis if missing data prevents assigning an unambiguous value to the DOOR endpoint or if the subject has not received at least one dose of study product. The CC-V1 cohort will consist of all subjects with sufficient data to define unambiguously the Visit #1 DOOR. The CC-V2 cohort will consist of all subjects with sufficient data to define unambiguously the Visit #2 DOOR.

According-to-Protocol Cohorts (ATP): Subjects in an ATP analysis require at least one dose of study product each day from Day 1 to Day 5 and furthermore subjects will be excluded from analysis if missing data prevents assigning an unambiguous value to the DOOR endpoint. The ATP-V1 cohort will restrict subjects to those with sufficient data to define unambiguously the Visit #1 DOOR. The ATP-V2 cohort will restrict subjects to those with sufficient data to define unambiguously the Visit #2 DOOR.

Details of what constitutes sufficient data to assign an unambiguous value to DOOR will be specified in the statistical analysis plan.

11.4.1 Primary Analysis

For the primary analyses, the DOORs will be compared between the 5- and 10-day arms. The sum of the probability that a randomly selected subject will have a better DOOR if assigned to the 5-day arm for Outcome Assessment Visit #1 plus one-half the probability of equal DOORs for Outcome Assessment Visit #1 will be estimated. The null hypothesis to be tested is that the probability is equal to 0.50 (lack of superiority of short-course therapy). The primary analysis will be carried out using the ITT cohort, with missing DOOR values (treated as continuous)

imputed using multiple imputation, utilizing linear regression models corresponding to relevant observed data (baseline covariates and observed DOOR components from an early termination visit, if available). The Mann-Whitney U statistic will be combined across the datasets to give the test statistic and Rubin's Rules used to define distribution of the test statistic under the null hypothesis. The test of the null hypothesis will be two-sided with a Type I error of 0.05. A point estimate of the estimand will be computed by dividing combined test statistic by the number of pairwise comparisons and a confidence interval of the estimand will be computed by inverting the described test of the null hypothesis.

Note: Subjects will be asked to confirm fever with repeat testing after approximately 15 minutes; for analysis purposes, subjects lacking a repeat measurement will be considered as having developed fever.

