5.3 Treatment Assignment Procedures

5.3.1 Randomization Procedures

Per International Conference on Harmonisation (ICH) guideline E6: Good Clinical Practice (GCP), screening records will be kept at each participating site to document the reason why an individual was screened, but failed trial entry criteria. The reasons why individuals failed screening will be recorded on screening logs maintained by each site.

Once consented and upon entry of demographic data and confirmation of eligibility for this trial, the subject will be enrolled. Subjects will be assigned to either placebo or active study drug (the same antibiotic that they were prescribed for the first 5 days of treatment). After a subject is enrolled, they will be given a random treatment assignment of study product to either short course or standard course therapy. Randomization to short vs. standard course therapy will be at a 1:1 ratio (approximately 200 subjects per treatment group). Subjects will be stratified by age group (<24 months vs. 24-71 months), type of initial antimicrobial therapy, and initial treatment in an ED or outpatient clinic/urgent care center.

Enrollment of subjects will be performed online using AdvantageEDC. The list of randomized treatment assignments will be prepared by statisticians at The Emmes Corporation and included in The Emmes Corporation's Internet Data Entry System (IDES). IDES will assign each volunteer a treatment code from the list after the necessary data have been entered into the system. A designated individual at each site will be provided with a treatment key, which links the treatment code to the actual treatment assignment, which will be kept in a secure place.

Instructions for subject enrollment are included in the Manual of Procedures (MOP). Manual back-up randomization procedures are provided in the MOP for use in the event that the site temporarily loses access to the Internet or the online enrollment system is unavailable.

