5. SAMPLE SIZE CONSIDERATIONS

The null hypothesis corresponding to the primary analysis of this study is:

H0: The sum of the probability that a subject assigned to the 5-day arm will have a higher DOOR than if assigned to the 10-day arm plus one-half the probability of equal DOORs is 50% (i.e., no difference in DOOR).

The primary study sample size is based on a superiority test of the null hypothesis above, under an assumed alternative hypothesis that the sum of the probability that a subject assigned to the 5-day arm will have a higher DOOR than if assigned to the 10-day arm plus one-half the probability of equal DOORs is 60% (p=60%).

A sample size of 360 (180 per arm) provides 90% power using a 2-sided alpha=0.05 with a Wilcoxon Mann-Whitney U test (see calculation below). If p=65% or 70%, then a total sample size of 160 (80 per arm) or 90 (45 per arm), respectively, would be required. The sample size is inflated by ~10% based on an estimate from a similar study, in order to account for loss to follow-up resulting in a total sample size of 400 (200/arm).

Sample size calculations were based on the formula below (Noether 1987):

$$N = \frac{(z_{\alpha} + z_{\beta})^2}{12c(1-c)\left(p'' - \frac{1}{2}\right)^2}$$

$$z_{\alpha} = \Phi^{-1}(0.975); z_{\beta} = \Phi^{-1}(0.90); (90\% \text{ power for two-sided test with } 5\% \text{ Type I error})$$

$$c = 0.5 \text{ (equal allocation to treatment arms)}$$

$$p'' = 0.6 \text{ (Pr(Higher DOOR) under alternative hypothesis)}$$

Note that the primary analysis statistical methods use the ITT analysis population and will account for missing data with multiple imputation. The exact analysis method was not used for the power calculation because it would require an excessive amount of assumptions about the nature and patterns of missing data in the final dataset and relationships of components of the imputation model to the primary outcome. Instead, a complete case analysis assuming 90% evaluable for analysis was used to obtain approximately 90% power in the actual analysis.

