6.5.7. Desirability of Outcome Ranking (DOOR) at OAV#1 or OAV#2

DOOR at OAV#1 is defined by ranking all subjects (pooling together both treatment arms) according to OCR at OAV#1 (lower is better) and using the number of days of antibiotic use at OAV#1 (lower is better) as a tie-breaker for comparing the ranking of two subjects with the same OCR. DOOR at OAV#2 is defined by ranking all subjects (pooling together both treatment arms) according to OCR at OAV#2 (lower is better) and using the number of days of antibiotic use at OAV#2 (lower is better) as a tie-breaker for comparing the ranking of two subjects with the same OCR. DOOR at OAV#1 or at OAV#2 is missing only if OCR or number of days of antibiotic use is missing for the respective OAV.

The ranking algorithm for DOOR is implemented as follows. A score variable is created that adds the number of days of antibiotic use (as defined in Section 6.5.6) divided by 100 to the OCR. Subjects are then ranked (DOOR) by the score, with the highest rank going to the subject with the lowest score, and the lowest rank going to the subject with the highest score. Tied scores result in a DOOR equal to the mean of the tied ranks. The algorithm is exemplified below using a simple scenario with 4 subjects.

Suppose Subject A has an OCR of 1 and 5 days of antibiotic use in the study period (score=1.05), Subject B has an OCR of 1 and 0 days of antibiotic use (score=1.00), Subject C has an OCR of 2 and 0 days of antibiotic use (score=2.00), and Subject D has an OCR of 1 and 5 days of antibiotic use (score=1.05). Because Subject B has the lowest score, Subject B is given DOOR=1 (the highest rank). Because Subject A and Subject D tie for the next lowest score, they both receive the mean of the next 2 available ranks (2 and 3, which has mean 2.5), and so the DOOR for both Subject A and Subject D is 2.5. Finally, Subject C has the highest score and therefore receives the worst available rank, which is DOOR=4.

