8.2.6.1. ITT Analyses of OCR at Outcomes Assessment Visit #1

Twenty (20) multiple imputation datasets for OCR at Outcome Assessment Visit #1 will be generated in manner analogous to that described in Section 8.1.1, except using OCR at Outcome Assessment Visit #1 in place of DOOR at Outcome Assessment Visit #1 for the response. Also, analogous to Section 8.1.1, the Mann-Whitney U statistic will be computed for each of the datasets and combined using Rubin’s Rules to generate the test statistic W and a p-value for the test of the null hypothesis that

$$\Pr(\text{OCR at Outcome Assessment Visit \#1 is better in short course}) + 0.5 \Pr(\text{OCR at Outcome Assessment Visit \#1 is equal}) = 0.5.$$

The F-test using the W statistic will be inverted to produce a 95% confidence interval for $\Pr(\text{OCR is better in short course}) + 0.5 \Pr(\text{OCR is equal})$. Whether the lower bound of this confidence interval is greater than 0.4 will serve as a test of the non-inferiority null hypothesis that

$$\Pr(\text{OCR at Outcome Assessment Visit \#1 is better in short course}) + 0.5 \Pr(\text{OCR at Outcome Assessment Visit \#1 is equal}) < 0.40.$$

Results will be reported in [Table 30](#).

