14.1.3 Prior and Concurrent Medical Conditions

Table 13: Summary of Subjects with Pre-Existing Medical Conditions by MedDRA System Organ Class and Treatment Group

MedDRA System Organ Class	Standard Course (N=X)		Short Course (N=X)		All Subjects (N=X)	
	n	%	n	%	n	%
Any SOC	x	xx	x	xx	x	xx
[SOC 1]						
[SOC 2]						

Note: N=Number of subjects enrolled; n = Number of subjects reporting medical history within the specified SOC. A subject is only counted once per SOC.

14.2 Efficacy/Immunogenicity Data**Table 14: Primary ITT Analysis of DOOR at Outcome Assessment Visit #1**

Statistic	Value
Subjects with all DOOR components measured – n (%)	x (x)
Subjects with one or more DOOR components imputed – n (%)	x (x)
Pr(Higher DOOR in Short-Course) ¹ (95% CI)	x.x (x.x – x.x)
P-value ²	x.xxx

¹ Probability of Higher DOOR in Short-Course Arm at Outcome Assessment Visit #1 + 0.5 Probability of Equal DOOR. Confidence interval obtained through inversion of the F-test used to compute the p-value.

² P-value boundary of 0.05 is used to conclude statistical significance. It is important to note that conclusions from DOOR analyses must rely on a detailed assessment of the DOOR components as well as consideration of sensitivity analyses, in addition to the statistical test described in this table.

Table 15: Primary ITT Analysis of DOOR at Outcome Assessment Visit #2

Statistic	Value
Subjects with all DOOR components measured – n (%)	x (x)
Subjects with one or more DOOR components imputed – n (%)	x (x)
Pr(Higher DOOR in Short-Course) ¹ (95% CI)	x.x (x.x – x.x)
P-value ²	x.xxx

1 Probability of Higher DOOR in Short-Course Arm at Outcome Assessment Visit #2 + 0.5 Probability of Equal DOOR. Confidence interval obtained through inversion of the F-test used to compute the p-value.

2 P-value boundary of 0.05 is used to conclude statistical significance. It is important to note that conclusions from DOOR analyses must rely on a detailed assessment of the DOOR components as well as consideration of sensitivity analyses, in addition to the statistical test described in this table.

Table 16: Sensitivity Analyses of DOOR at Outcome Assessment Visit #1

Analysis	Pr (Higher DOOR) ¹	Normal Approx. 95% CI ²	Bootstrapped 95% CI ³	P-value ⁴
Complete Case (CC-V1)				
According-to-Protocol (ATP-V1)				
Worst Case (ITT)				

¹ Probability of Higher DOOR in Short-Course Arm at Outcome Assessment Visit #1 + 0.5 Probability of Equal DOOR.

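### Rejecting 0.50 on DOOR shows neither clinical superiority nor absence of clinical harm, because the antibiotic-day tie-break alone gives about 0.5 + T/2 (T = OCR tie share); the claim should also require the planned OCR non-inferiority result

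*Protocol*

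**What the plan says.** **Final test.** Protocol 11.4.1: "The null hypothesis to be tested is that the probability is equal to 0.50 (lack of superiority of short-course therapy". It adds: "The test of the null hypothesis will be two-sided with a Type I error of 0.05". SAP Table 14, footnote 2, repeats the criterion: "P-value boundary of 0.05 is used to conclude statistical significance". The same footnote then says that conclusions must rest on the DOOR components and the sensitivity analyses as well. It names no component, threshold or rule.

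**Planning value.** SAP section 5 assumes that the probability of a higher DOOR on the 5-day arm "plus one-half the probability of equal DOORs is 60% (p=60", and states: "A sample size of 360 (180 per arm) provides 90% power using a 2-sided alpha=0.05 with a Wilcoxon Mann-Whitney U test".

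**How DOOR is built.** SAP 6.5.7 ranks children on OCR (8 levels), "using the number of days of antibiotic use at OAV#1 (lower is better) as a tie-breaker". SAP 3.3 limits the Visit #1 count of antibiotic days to Days 1-5, which is the randomized period. Under SAP 6.5.6 placebo days count as zero unless a systemic antibiotic is recorded, and any dose of active study product counts as a day.

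**OCR alone.** SAP 8.2.6.1 compares OCR with 0.50 and adds a margin: "Whether the lower bound of this confidence interval is greater than 0.4 will serve as a test of the non-inferiority null hypothesis". This is a secondary analysis. Protocol 11.4.2 leaves non-inferiority analyses of OCR optional.

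**The concern.** Protocol 2.3.1 names the open question: clinical outcomes on the short course might not match those on the standard course, and the trial is to evaluate that risk. Lower antibiotic exposure is not open in the same way, because the randomized assignment largely delivers it. The final rule merges the two, and its DOOR component starts well above 0.50 when the clinical outcomes are identical.

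Neither document gives the DOOR value expected under equal OCR, or says how much of the planned 60% is tie-break. A reader told that short course was superior, in a trial with 90% power, could take that as a clinical finding. The rule does not support that reading, and it can also pass when short course is clinically somewhat worse.

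**Working it through.** **Inputs.** Null 0.50, two-sided alpha 0.05 (Protocol 11.4.1); alternative 0.60, 180 per arm (SAP 5); 1:1 allocation (Protocol 5.3.1); 8 OCR levels and fewer days winning ties (SAP 3.3, 6.5.7). The documents give no OCR distribution, so every mix below is an assumption.

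**1. The plan's own figure.** Noether: N = (1.960 + 1.282)² / [12 × 0.25 × (0.60 − 0.50)²] = 350, against 360 stated. At N = 360, power = Φ(√(3 × 360) × 0.10 − 1.96) = 90.8%. The stated figure reproduces.

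**2. DOOR with no clinical effect.** If every short-course child has 0 days and every standard-course child 5, short course wins every OCR tie:

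DOOR = (OCR probability) + T/2 = 0.50 + T/2, with T = Σp²

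Over 8 levels Σp² is smallest for a uniform mix: T = 1/8 and DOOR = 0.5625. The smallest significant estimate at N = 360, ignoring ties, is 0.5 + 1.96/√1080 = 0.560.

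**3. What 60% means.** The implied OCR probability is 0.60 − T/2. It is below 0.50 once T exceeds 0.20, and equals 0.40, the SAP's margin, at T = 0.40. One level holding 45% of children already gives T of at least 0.45² = 0.20.

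**4. How often the rule favours short course with no clinical effect.** Simulated at 180 per arm, correctly tie-corrected Mann-Whitney, no missing data:

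| Assumed OCR mix, levels 1-8 (%) | T | DOOR | DOOR rule alone | DOOR rule and OCR limit > 0.40 |
|---|---|---|---|---|
| 12.5 in each | 0.125 | 0.5625 | 54% | 53-54% |
| 25/25/20/10/15/4/1/0 | 0.20 | 0.60 | 89-91% | 89-91% |
| 40/25/15/5/10/4/1/0 | 0.26 | 0.63 | 99% | 92-93% |
| 50/22/10/3/10/4/1/0 | 0.32 | 0.66 | about 100% | 94% |

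**5. Imperfect separation of days.** With 2% to 10% crossover or undosed children, the uniform case falls to 0.561-0.554 (52%-44%) and the 25/25/20 mix to 90%-82%. Rescue antibiotics weaken the tie-break in OCR 6-7. If it is neutral in OCR 6-8 and the other five levels are equally filled, 5%, 10% or 20% of children in OCR 6-8 gives 0.590, 0.581 or 0.564 (85%, 76%, 56%). An extreme 37.5% there gives 0.539 (25%).

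**6. Harm.** Standard arm 50/22/10/3/10/4/1/0, with 10 points of short-course children moved from OCR 1-4 to OCR 5-7. The OCR probability is about 0.45 and T about 0.29, so DOOR is about 0.45 + 0.146 = 0.596. The DOOR rule favours short course in about 87% to 89%; with the OCR limit added, about 42%. The size depends on the mix. Moving 10% of short-course children to OCR 6 (OCR probability 0.453) gives 66% in the 40/25/15 mix and 32% in the 25/25/20 mix. Moving 5% (0.477) gives 91% and 66%.

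**7. Can the OCR test be computed as written?** SAP 8.2.6.1 reuses the variance of SAP 8.1.1, whose tie term has no divisor as the formula reads there: (n₁n₂/12)[(n₁ + n₂ + 1) − Σ(M³ − M)]. For the 50/22/10 mix the pooled OCR counts are 180, 79.2, 36, 10.8, 36, 14.4 and 3.6, so Σ(M³ − M) is about 6,426,000. The variance is 2,700 × (361 − 6,426,000), about −1.7 × 10¹⁰. Dividing the tie term by N(N − 1) = 360 × 359 = 129,240 gives 2,700 × (361 − 49.7), about 840,000. DOOR itself fails in the same way: splitting each level by 0 or 5 days halves the counts, Σ(M³ − M) is about 1,606,000, and the variance is again negative.

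**The case against.** The strongest reply is that this is the estimand the trial chose. Protocol section 11 says that RADAR weighs all important outcomes together and lists antibiotic duration among them, and the tie-break is defined openly. That stands. A reader might infer from the table above that 0.50 is the wrong null, or that these are false positives. The documents do not support either reading: DOOR truly exceeds 0.50 in those trials, so rejecting is correct for DOOR and alpha is preserved.

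A reader might also treat 0.5625 and 54% as strict floors. They are not. SAP 6.5.6 counts days actually taken, including non-study antibiotics, so crossover and rescue lower both figures. The uniform mix is also unrealistic, since it puts 12.5% of children in the death category. Clustered mixes are more plausible: Protocol 2.2 reports no treatment failures at 5 or 10 days in the earlier trial it cites.

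The SAP already plans the OCR-only tests, an exploratory analysis without the tie-break (k = infinity, SAP 8.3.1) and analyses of each component. The split into an OCR part and a tie-break part can therefore be read from Tables 14 and 30, or from Table 46, and needs no new output. But none of these results is tied to the final claim.

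The added condition has limits too. The documents do not justify 0.40, and meeting it shows non-inferiority within that margin, not clinical superiority. An OCR probability of 0.45 lies inside the margin, so the remaining 42% is expected behaviour of that test.

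**Conclusion.** The point holds as one of interpretation and decision rule, not of test validity. With equal OCR in both arms DOOR is about 0.5 + T/2, slightly less with crossover or rescue antibiotics. For the assumed clustered mixes this is 0.60 to 0.66, and the primary rule favours short course in about 89% to 100% of trials. It did so in about 87% to 89% under the main harm scenario, and less often under other assumed mixes. A rejection therefore shows superiority on a composite that includes antibiotic days. It establishes neither clinical superiority nor absence of clinical harm, and Table 14's instruction to rely on components has no rule behind it.

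These figures rest on assumed OCR distributions, 180 complete cases per arm and, except in step 5, full separation of days. Multiple imputation was not simulated. The identity, and the 0.20 threshold for T under full separation, do not depend on the mix.

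**What to change.** - **Protocol 11.4.1, SAP 8.1.1 and Table 14:** conclude in favour of short course only if DOOR has p < 0.05 with an estimate above 0.5 and the Visit #1 OCR non-inferiority test of SAP 8.2.6.1 is met (lower limit above 0.40). Both are required, so no alpha is split.
- **Protocol 11.4.2:** make that OCR non-inferiority analysis a commitment instead of an option.
- **SAP 8.1.1, and the same formula in 8.2.1 and 8.2.2:** divide the tie term by N(N − 1), so that both tests can be computed.
- **Reporting:** if only the DOOR condition is met, describe the result as superiority on the composite including antibiotic days.
- **SAP 5:** state that equal OCR gives about 0.5 + T/2, so that 60% implies better OCR only if T is below about 0.20.

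**Cost:** wording and one formula; no new data and no new margin. With no clinical effect the chance of a positive claim becomes about 89% to 95% in the clustered mixes. The condition reduces claims under the main harm scenario (about 89% to about 42%) but does not remove them.
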